### **Design Summary**

The main objectives of this study are to assess the effects of bupropion and nortriptyline on smokers' emotional reactivity during a quit attempt, as assessed by startle responding to positive and negative emotional cues, and smoking related stimuli; whether this emotional reactivity predicts time to relapse; and, if genetic differences influence the magnitude of these effects. The present study will use a 3x4x4 repeated measures design, with Group (Bupropion/Nortriptyline/ Placebo) serving as the between groups factor, and Days (days post-quit/laboratory assessments) and stimulus valence (positive, negative, neutral, cigarette) serving as within subject factors. The sample will be stratified for race, gender, previous history of major depression, and the DRD2A1/A2 genotype, since the DRD2 marker is of primary interest. As shown Figure 6, 354 smokers will be exposed to four laboratory assessment sessions over a period of 38 days. Medication will be administered in a blinded fashion. Participants will complete a baseline laboratory session before any treatment begins (while still smoking). Immediately after their baseline laboratory session participants will be randomized into one of the three treatments and begin taking the appropriate medication. After ten days of medication, all groups will quit smoking for the duration of the study. Participants in all groups will also receive a series of in-person smoking cessation counseling sessions, two prior to quitting and five after the quit date, plus a series of telephone counseling calls at selected intervals in between the in-person counseling sessions. After completion of all laboratory and counseling sessions, all participants will return for follow up assessments at 3

months (10 days after medication ends) and 6 months post quit. In addition, telephone assessments of abstinence status will be carried out 2 and 4 months post-quit. A study time line is provided on page 20.

**Subject Recruitment.** Participants who want to quit smoking will be recruited from Houston

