### Medication Blinding

Medications will be supplied by the Drug Product Services Laboratory in the Department of Clinical Pharmacy, University of California, San Francisco (see letter of support section I). This pharmacy made the nortriptyline and bupropion placebo preparations used in [name] nortriptyline and bupropion research studies and has agreed to provide our study with similar preparations. To keep all medications similar in appearance, active and placebo formulations will be enclosed in unmarked sealed and brushed capsules and shipped to MD Anderson Department of Experimental Therapeutics Research Pharmacy for patient distribution. The MD Anderson pharmacy will implement the randomization schedule as developed by the study statistician. Because nortriptyline levels can only be detected in the nortriptyline group, only the study

physician (and his staff) will be un-blinded as to treatment condition, as they will be responsible for the dose titration and medication checks. Our study physician will not be involved in the counseling or startle assessments and he or a member of his staff will conduct the adverse reports assessments. All other members of the research team will remain blind to treatment condition.

To maintain the integrity of the blind among the participants themselves and the other research staff, about 10% of all participants in the placebo and bupropion groups will also undergo the same schedule of blood analysis as the nortriptyline group. We feel this is an appropriate compromise to maintain a blinded research protocol and at the same time, minimize the risk of unnecessary blood draws among the bupropion and placebo groups. The code for who will be selected for the blood draw will be imbedded in the randomization schedule. Medication will be un-blinded in the event of drug related a serious adverse event, Abstinence Compliance and Startle Assessments

[figure not shown]

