## Power

Analysis of the startle responses will be conducted using mixed model regression. The study design involves both between subject and within subject fixed effects and correlations due to repeated measures on the participants. Within subject fixed effects include Days (baseline, post quit days 2,5, 28) and slide valence (positive, negative, neutral, cigarette). Between subjects effects include Treatment (Placebo, Bupropion, Nortriptyline) and Genotype (e.g., A1/A1 or A1/A2 and A2/A2 for our main hypothesis, and others as described for secondary hypotheses). Because of the nonstandard design, power calculations were conducted using simulations in SAS (PROC MIXED). To simplify calculations, we

**Table 4 Effect Sizes & Corresponding Differences in Startle Magnitude (µVolts) For Comparisons Genotype Main Effects Varying Prevalence Rates of the At Risk Allele**

Prevalence of "at risk" allele	Model 1	Model 2	Model 3
.5	.15 (3)	.29 (20)	.29 (16)
.4	.16 (3)	.30 (20)	.30 (16)
.3	.17 (4)	.32 (22)	.31 (17)
.2	.20 (4)	.36 (25)	.35 (19)

assume that the response to the slides at each level of valence within session will be averaged. The repeated measures on each subject are associated with correlations between observations from the same subject across sessions, and between observations from the same subject within session. We estimated these correlations using data from our previous work. For the primary hypothesis described below, we will fit three models. The first (Model 1) will restrict analyses to positive, negative and cigarette, stimuli and use the score to the neutral stimuli as a covariate, the second (Model 2) will use data from all valences together, and the third (Model 3) will use all data but examine post-quit scores controlling for baseline scores. The within subject-between-session and within subject-within session correlations varied for each model in our preliminary work. For Model 1, we estimated the within subject-between session and within subject-within session correlations to be .03 and .45, respectively; for the Model 2 we estimated them to be .7 and .9, respectively, and for Model3, we estimated them to be .6 and .9, respectively.

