  - 1.1. Mixed model repeated measure regression analyses will be used to evaluate this hypothesis, regressing peak startle magnitude, on Group (Bupropion, Nortriptyline, Placebo with Days (e.g., baseline, post-quit days 2, 5, 28) as the repeated measures factor. Three types of models will be evaluated. Model 1 will be restricted to startle responses to positive negative and cigarette stimuli and will include valence (positive/negative/cigarette) as a factor. This model will also include the corresponding value of the startle response to neutral stimuli as a covariate. In this way, we can compare the relative magnitude of startle responses to each valence adjusted for the response to neutral cues. The main effect of treatment Group is of primary interest in this model and will be evaluated first, followed by Days, and the Group X Day interaction. Other interactions including Group X Valence and Group X Valence X Days will also be explored. To assess Group differences (if any) at the beginning of the study, an a priori contrast on the baseline values only will also be carried out for this model, evaluating the main effect of Group and the Group by Valence interaction. In Model 2, startle will not be restricted to positive, negative or cigarette valences but will include all valences. The main effect of Group will be evaluated first, followed by Days, each of the two way interaction terms, and the Group X Day X Valence interaction. An a priori contrast will also be carried out as in Model 1 on the baseline values, to assess Group differences (if any) at the beginning of the study. The third model will involve only the post-quit assessments. This model is similar to Model 2, but will include the corresponding baseline value for each stimulus valence as a covariate. In this way, post cessation startle values may be expressed as a function of the corresponding pre cessation baseline values. As described in our preliminary studies, we believe this analysis can be quite informative, as it focuses on post cessation startle in relation to responses under nondeprived (baseline) conditions.
2. The emotional reactivity of smokers during cessation will be moderated by genotype. Our initial hypotheses focuses on the DRD2:
  - 2.1. We hypothesize that emotional reactivity will be lower for those carrying the DRD2 A1 and using bupropion vs. A1 smokers using either nortriptyline or placebo. A1 nortriptyline users are expected to

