have lower reactivity than A1 placebo users[PCP18]. Homozygous A2s are expected to respond similarly to both drugs with higher levels of emotional reactivity being observed for placebo vs. either bupropion or nortriptyline.

This hypothesis will be evaluated using models similar to those described for hypothesis 1, but with the addition of Genotype (A1/A2 or A1/A1 vs. A2/A2) as a term in each model. We will specifically evaluate the main effect of Genotype first, followed by the Genotype X Group interaction (the term of interest). Other interactions involving Genotype with Days and Valence will be explored as described for Models 2 and 3 above. Planned contrasts involving the difference in startle magnitude between each Group condition, within Genotype, will also be carried out.

3. Higher levels of emotional reactivity of smokers at baseline and or during cessation will be inversely related to abstinence at the 3 and 6 month follow-ups.

- 3.1. Two types of analysis will be carried out. Our primary focus will be on predicting days to relapse. For this analysis, startle responses will serve as the independent variable with days to relapse as the dependent measure. The primary analysis will focus on the average startle response from the baseline assessment. In secondary models, average response to each valence will be included as predictors to determine the relative predictive strength of the different valences. Startle response from each of the post-quit assessments will also be examined as time dependent variables to determine if startle responses from the other assessments predicts relapse. Each model will also be evaluated controlling for or not controlling for treatment Group. For this analysis we will use Cox proportional hazards regression. We are also interested in predicting abstinence (yes/no) at the 3 and 6 month follow-up. Therefore we will also use the GLIMMIX Macro from SAS, which is an adaptation of the PROC Mixed procedure for hypothesis 1 and 2 for dichotomous out come variables (abstinence) to test whether startle responses are related to abstinence, modeling baseline, valence and time dependent characteristics of the model in the manner proposed above. Interactions between genotype (DRD2 A1 vs. A2) and startle in the prediction of abstinence, will also be explored using in the separate and combined valence models.

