Covariates will be included in all models described above to correct for any baseline differences and help improve power. The covariates to be used include ethnicity, age, gender, smoking history, and depression history. Interactions between ethnicity or gender and genotype will be explored. If we find statistically significant interactions, separate models for each ethnicity or gender will also be tested.

The contribution of the WSWS, CES-D, PANAS scores and in-session ratings of craving and mood, to the observed startle effects in the primary hypotheses will be explored by fitting these variables as covariates in the above models. In addition we will examine the relationship between these measures, startle values for each valence, and with in sessions affect ratings using correlational procedures. Changes in these measures over time will also be evaluated using the same Mixed Model approach described above with Group and Genotype serving as between groups factors and Days as the repeated measure. Finally, the primary analyses of the startle magnitude described above will be repeated on the changes in skin conductance response and heart rate to determine the pattern of autonomic arousal displayed for baseline and withdrawal conditions.

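### DRD2 genotype is the only stated stratification factor missing from the covariate list, so the hypothesis 1 Group test gives up a small, free gain in precision (no bias)

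*Combined protocol and SAP*

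**What the plan says.** The Design Summary states: "The sample will be stratified for race, gender, previous history of major depression, and the DRD2A1/A2 genotype". It gives the primary interest in DRD2 as the reason for including that factor. Medication Blinding adds only "The MD Anderson pharmacy will implement the randomization schedule as developed by the study statistician". Neither section says how, or whether, the strata enter the randomisation.

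Under Primary Hypotheses, item 1.1 regresses startle magnitude on Group with Days as the repeated factor, in three models. The main effect of Group is the term of primary interest in Model 1, and for Model 2 the order is "The main effect of Group will be evaluated first, followed by Days, each of the two way interaction terms". None of the three models contains Genotype. Item 2.1 reuses similar models for hypothesis 2 and adds Genotype (A1 carrier v A2/A2) to each, with Genotype X Group as the term of interest.

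The covariate paragraph then says "Covariates will be included in all models described above to correct for any baseline differences and help improve power", followed by "The covariates to be used include ethnicity, age, gender, smoking history, and depression history".

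Elsewhere the plan puts treatment and genotype together. The Power section says "Between subjects effects include Treatment (Placebo, Bupropion, Nortriptyline) and Genotype". The mood and withdrawal measures are to be modelled "with Group and Genotype serving as between groups factors and Days as the repeated measure".

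**The concern.** Three of the four stratification factors are on the covariate list (race appears as ethnicity). The missing one is the factor that the plan singles out.

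DRD2 also meets the plan's own reason for adjusting. In Preliminary Studies, A1 carriers had higher baseline startle (p=0.0005), and the effect remained after controlling for gender or race. The same pilot found no significant main effect of gender or race on baseline startle, yet both are on the list.

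Leaving a prognostic stratification factor out of a linear model has a known effect. If randomisation is balanced on the factor, the model's reported standard error includes between-genotype variance that the design has already removed from the comparison. The test is then slightly conservative. If randomisation is simple, the error rate is nominal and the precision is lost. In both cases what is at stake is a little power for the hypothesis 1 Group contrast.

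**Working it through.** **Inputs**
- 354 participants, taken as 118 per arm (1:1:1 assumed), with alpha 0.05 taken as two-sided. The detectable Group effect in Model 2 is .32 SD or 22 µV (Power).
- Model 2 correlations: .7 between sessions and .9 within session (Power), with 4 valences and 4 sessions.
- A1 carriers: 42.6% of smokers (Table 3), rounded to .43.
- A1–A2 difference: 26 µV among pilot smokers who quit (Power), from a pilot with 62 genotyped (Preliminary Studies). Two illustrative values are added: 20 µV, the Model 2 detectable difference in Table 4 at prevalence .4 to .5, and 16 µV, which is assumed.

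**1. The plan's own figure for Model 2**
- SD: 22/.32 = 68.8, 41/.60 = 68.3, 43/.63 = 68.3 and 39/.57 = 68.4, so about 68.5 µV.
- Variance of a participant's mean: (1 + 3×.9 + 12×.7)/16 = .756; .756 × 68.5² ≈ 3549.
- SE of a two-arm contrast: √(2×3549/118) = 7.76 µV.
- Standardised effect: λ = .32×68.5/7.76 = 21.92/7.76 = 2.83.
- Power: Φ(2.83 − 1.96) = 80.7%, which agrees with the stated 80%.

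**2. Share of variance due to genotype**

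R² = d² × .43 × .57 / 3549
- 26 µV: 165.7/3549 = 4.7%
- 20 µV: 98.0/3549 = 2.8%
- 16 µV: 62.7/3549 = 1.8%

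**3. Power and error with and without DRD2**
- Adjusted: Φ(λ/√(1−R²) − 1.96).
- Unadjusted, stratified randomisation: power Φ((λ−1.96)/√(1−R²)); type I error 2×(1−Φ(1.96/√(1−R²))).
- Unadjusted, simple randomisation: power 80.7%; type I error 5.0%.

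| A1–A2 difference | Type I, stratified, unadjusted | Power, stratified, unadjusted | Power, simple, unadjusted | Power, adjusted |
|---|---|---|---|---|
| 26 µV | 4.5% | 81.3% | 80.7% | 82.5% |
| 20 µV | 4.7% | 81.0% | 80.7% | 81.8% |
| 16 µV | 4.8% | 80.9% | 80.7% | 81.4% |

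At 26 µV under stratification, the reported SE is about 2.4% too wide (1/√(1−.047) = 1.024). Under simple randomisation the gain equals 354×(1/(1−R²) − 1), or about 17, 10 and 6 extra participants at 26, 20 and 16 µV.

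**4. Simulation check**

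With three arms of 118 and a 26 µV difference, the unadjusted and adjusted tests compare as follows:
- Stratified (200,000 trials): type I error 4.4% v 5.0%; power 81.1% v 82.3%.
- Simple (100,000 trials): type I error 5.1% v 5.0%; power 80.7% v 82.5%.

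A separate run of 20,000 trials with R² = 4.6% and balanced strata gave a mean estimate of −0.365, against a true −0.365, with and without genotype. There is no bias.

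**5. Models 1 and 3**

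No size is given. The raw 26 µV cannot be carried to Model 1's neutral-adjusted scale, where it would imply an R² above 1. Model 3 already conditions on baseline startle, which absorbs an unknown part of the genotype difference.

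**The case against.** The strongest case against is that this is a preference and not an error. The unadjusted test is valid, the covariate list is stated in advance, and the gain is about one or two points at most. That stands, and it fixes the rating at optional.

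The size is also less certain than the arithmetic suggests:
- Only 26 µV is observed. It comes from a small pilot and from smokers who quit, so it is near an upper value.
- The calculation starts from total variance, before ethnicity, age, gender, smoking history and depression history are fitted. The pilot's association between A1 and race had p=0.08, so genotype's contribution beyond those covariates is unknown and could be smaller or larger. Some gain remains plausible, because the pilot genotype effect survived control for gender or race.
- The Power section lists Genotype among the between-subjects effects, so the 68.5 µV SD may already exclude genotype variance. This hardly matters. R² at 26 µV becomes 165.7/(3549+165.7) = 4.5%, and the unadjusted SE is √(2×3714.7/118) = 7.93 µV. Unadjusted power is then Φ(21.92/7.93 − 1.96) = 78.9% if simple, or Φ((21.92 − 1.96×7.93)/7.76) = 79.4% if stratified, against 80.7% adjusted. The gain is again 1.3 to 1.8 points.

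One could also argue that the word include leaves the covariate list open. Item 2.1 answers this: Genotype is described there as an addition to models like those of hypothesis 1.

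Three stronger readings are tempting, and the documents do not support them:
- A reader might infer that it is unclear which fit is the hypothesis 1 test. Items 1.1 and 2.1 together identify it as the fit without Genotype.
- A reader might take 20 µV as the plan's expected genotype difference. Table 4 gives it as a detectable difference.
- A reader might apply these figures to every hypothesis 1 model. They hold for Model 2 only.

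**Conclusion.** The point holds as a free improvement. DRD2 is a stated stratification factor, the pilot links it to startle, and it is the only such factor left out of the hypothesis 1 models.

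A reader might infer that the Group estimate is biased or its type I error inflated. Neither is so: the estimate is unbiased, and the error is nominal or slightly below nominal.

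For Model 2, before the other covariates, the loss is 1.2 points of power at 26 µV if randomisation is stratified on genotype and 1.8 points if it is simple. At 20 and 16 µV it is about 0.5 to 1.1 points. These figures assume 118 per arm, a two-sided 0.05 test, 43% A1 carriers and the plan's Model 2 correlations.

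The omission itself is clear from the text. Confidence in the size of the gain is moderate, and no size is established for Models 1 and 3.

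**What to change.** In the covariate paragraph under Primary Hypotheses, add DRD2 genotype (A1 carrier v A2/A2) as a main-effect covariate for the hypothesis 1 models. State that the hypothesis 1 Group test comes from that model, without Genotype X Group. The interaction stays where it is, in hypothesis 2.

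The cost is one line in the SAP and one degree of freedom. No new data are needed: blood for genotyping is taken at the orientation visit, and hypothesis 2 already requires the result.

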Lerman and her colleagues investigated the interaction of the dopamine transporter gene (DAT), SLC6A3-9 and the DRD2 A1 on smoking behavior. The SLC6A3 gene regulates synaptic dopamine by coding for a re-uptake protein called DAT. It has a 3' variable number tandem repeat (VNTR; 40 bp) polymorphism^32. Smokers with the SLC6A3-9 allele started smoking later and quit for a longer time than those without it. These effects were not modified by DRD2 status and the SLC6A3-9 was not associated with Fagerstrom dependence scores. However, the SLC6A3-9 repeat was more frequent among Caucasian nonsmokers (62%) who also had the A2 allele but not among those who had the A1 allele (46%). Similar but non-significant trends were noted for African American smokers. It appears that the "protective" effect of the SLC6A3-9 for smoking (greater frequency among nonsmokers vs. smokers) is eliminated by the presence of the A1 allele. Similar findings have been reported by Sabol et al., who found the odds of smoking cessation (i.e., being a former

vs. current smoker) was higher for those having the SLC6A3-9 allele (51.9% vs. 42%). Smoking rates were also higher for participants carrying the A1 allele, and more people quit who had SLC6A3-9 and did not have the DRD2 A1 allele, although these effects were not statistically significant. However, the relationship between smoking and the DAT was not replicated in a large Australian study using a non-clinical sample or in a US community based sample.

Studies have also associated the DRD4 receptor (a member of the D2 family of receptors) with smoking. The data suggest that the long form of the gene is associated with a blunted response to dopamine and higher scores on the Tridimensional Personality Questionnaire "Novelty-Seeking" subscale, among smokers. The long form of the gene (S/L or L/L) is comprised of 6-8 repeats, of which 7 is most common while the short form (S/S) consists of 2-5 repeats with 4 being the most frequent. A study by Shields, et al., found that the long allele was more frequent among African American vs. Caucasian smokers. African Americans with this allele were more likely to be smokers, are less likely to quit, started smoking at an earlier age, and smoked more often within 30 min of waking than those with the short form.

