**Figure 6 Design Summary and Study Flow**

metropolitan area using newspaper, radio and TV public service announcements, feature articles in the MD Anderson newsletter, and posted flyers. They will be offered monetary compensation for their time and for maintaining their abstinence. We expect to have no difficulty recruiting the needed number of smokers. The psychophysiology laboratory is a resource of the MDACC Tobacco Research and Treatment Program (TRTP). The TRTP is directed by the PI and has a high degree of community visibility. We have had considerable success recruiting participants for our clinical trials research.

**Population Description** The population of the greater Houston community from which the sample will be drawn (Harris and its 6 adjacent counties) is estimated at 4,636,908 people. The ethnic distribution has been reported as 73.5% Caucasian; 18.4% Hispanic or Latino (of any race); 12.6% African-American; 3.2%

Asian; and .5% Native American,. Although the literature on the relationship of the DRD2 A1 allele to alcoholism^152, cocaine, other substance abuse, and smoking has been largely limited to Non-Hispanic Caucasians and some studies with African Americans, we will recruit without regard to race or ethnicity, as we did in our preliminary studies. As described in the Inclusion Enrollment Report (see Table 6) we have had reasonable success recruiting from ethnic minority populations.

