**Table 7 Targeted/Planned Enrollment Table**

**Study Title:** Pharmacogenetics and Smoking Therapy

**Total Planned Enrollment:** 354

TARGETED/PLANNED ENROLLMENT: Number of Subjects			
Ethnic Category	Sex/Gender		
	Females	Males	Total
Hispanic or Latino	29	28	57
Not Hispanic or Latino	148	149	237
Ethnic Category Total of All Subjects*	177	177	354
Racial Categories			
American Indian/Alaska Native	0	0	0
Asian	20	20	40
Native Hawaiian or Other Pacific Islander	0	0	0
Black or African American	57	57	114
White	120	120	240
Racial Categories: Total of All Subjects *	177	177	354

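### The genotype-by-drug models omit Ethnicity x Group, so if genotype frequency and drug response both differed by ethnicity, the planned adjustment could not separate the two

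*Combined protocol and SAP*

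**What the plan says.** - **Test of interest.** For Hypothesis 2 (Primary Hypotheses), the genotype main effect is evaluated first, "followed by the Genotype X Group interaction (the term of interest").
- **Covariates.** For all primary models: "The covariates to be used include ethnicity, age, gender, smoking history, and depression history". The stated purposes are to correct baseline differences and improve power.
- **Ethnicity interactions.** "Interactions between ethnicity or gender and genotype will be explored". The next sentence adds a conditional step: "If we find statistically significant interactions, separate models for each ethnicity or gender will also be tested".
- **Design.** "The sample will be stratified for race, gender, previous history of major depression, and the DRD2A1/A2 genotype" (Design Summary). On recruitment, the population description says "we will recruit without regard to race or ethnicity, as we did in our preliminary studies". Table 7 plans 114 participants in the row "Black or African American" out of 354. The race rows of that table add to 394 (40 + 114 + 240), so the share is approximate: 32% on 354, 29% on 394.
- **Genotype by race.** Section C reports that A1 carriage in the pilot did not differ by race (chi-square 3.1, p = 0.08; DRD2 available on 62). Inclusion of Minorities calls the distributions with and without A1 comparable. For DRD4, the background says one study "found that the long allele was more frequent among African American vs. Caucasian smokers".
- **Other markers.** Secondary Analyses Involving Other Markers repeats the same mixed models for DRD4, SERT, DAT and NET.

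Ethnicity x Group is not mentioned anywhere.

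**The concern.** Randomisation, with or without stratification by race, makes ethnicity similar across the three arms. It does not make ethnicity similar between A1 carriers and A2 homozygotes, because genotype is not randomised. If one ethnic group responds differently to a drug and is also over-represented among A1 carriers, the drug effect will differ between genotypes even when the gene plays no part.

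The planned terms address other questions. An ethnicity main effect removes differences in the level of startle. Ethnicity x Genotype lets the genotype difference in level vary by ethnicity. Neither lets the drug effect vary by ethnicity. Ethnicity-specific models would help, but their trigger is a significant ethnicity-by-genotype (or gender-by-genotype) interaction. That interaction can be absent when the confounding is present.

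The trial's stated purpose is to inform matching of treatments to genotype. Attributing an ethnic difference in drug response to a gene would undermine that use.

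**Working it through.** **1. The bias.** Take one drug against placebo, genotype g and ethnicity indicator E. Let the drug effect be τ + γg + δE. Averaged over E within genotype it is τ + γg + δP(E|g), so without Ethnicity x Group the interaction estimates

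γ + δ[P(E|A1) − P(E|A2)].

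Group is randomised independently of g and E. With Group centred, Group x E is therefore uncorrelated with E and with g x E, and adding those two terms leaves the bias in place. If either δ or the bracket is zero, there is no bias.

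**2. Simulation check.** 3,000 runs per scenario, 118 v 118, subject means, Model 2 correlations, no true gene-by-drug effect. Assumed: two ethnic groups, 32% in one.

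| A1 frequency by ethnicity | δ (SD) | Type I error: E only | E and G x E | E x Group added |
|---|---|---|---|---|
| 0.426 v 0.426 | 1.0 | 4.9% | 5.0% | 4.9% |
| 0.55 v 0.37 | 0.6 | 7.6% | 7.9% | 5.5% |
| 0.55 v 0.37 | 1.0 | 10.1% | 10.1% | 5.0% |

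At 0.55 v 0.37 and 0.6 SD, the bias is 0.099 SD in magnitude with or without G x E, and about 0 with E x Group. These scenarios show the mechanism, not a likely size: 0.6 and 1.0 SD are 1.9 and 3.1 times the 0.32 SD drug effect that Model 2 is powered for. At A1 0.50 v 0.39 and δ = 0.3 SD, the analytic type I error is 5.8%, 5.2% and 5.2% for Models 1, 2 and 3.

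**3. Calibration to the plan.** The plan states no figure on this point, so its Hypothesis 1 effect size was reproduced. For Model 3 (3 sessions, 4 valences, correlations 0.6 and 0.9), the SD of a subject mean is √[(1 + 3×0.9 + 2×4×0.6)/12] = √(8.5/12) = 0.842. The detectable difference is 2.80 × 0.842 × √(2/118) = 0.307 SD, against 0.30 stated.

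**4. Standard error of Genotype x Group, Model 3.**
- From Table 5 at prevalence 0.4: 32 µV at 80% power gives 32/2.80 = 11.4 µV.
- Closed form, one drug v placebo: 2.80 × 0.842 × √[(2/118)/(0.4×0.6)] ≈ 0.627 SD. At 32/0.59 = 54.2 µV per SD this is 34.0 µV, and 34.0/2.80 = 12.1 µV.

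**5. The genotype-ethnicity difference for DRD2.** Pilot phi = √(3.1/62) = 0.224. Approximate 95% interval: atanh(0.224) ± 1.96/√59 = 0.2275 ± 0.2552, which transforms back to −0.03 to 0.45. Phi is close to the difference in ethnic mix: with a 32% share and 43% carriers, 0.224 × √[(0.32×0.68)/(0.43×0.57)] = 0.21.

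**6. Hypothetical size.** Bias = 0.224δ; k = bias/SE; two-sided type I error = Φ(−1.96 − k) + Φ(−1.96 + k). The values of δ are assumptions.

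| δ (µV) | Bias (µV) | Type I error, SE 11.4 to 12.1 |
|---|---|---|
| 0 | 0 | 5% |
| 8 | 1.8 | 5.3% |
| 16 | 3.6 | 6.0-6.1% |
| 20 | 4.5 | 6.6-6.8% |
| 40 | 8.9 | 11-12% |

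For scale, Model 3 is powered for a drug effect of 16 µV, so 20 and 40 µV are 1.25 and 2.5 times that whole effect. At the upper limit of phi, δ = 16 gives 0.45 × 16 = 7.2 µV, k = 7.2/11.4 = 0.63, and type I error of 9.7%. At the lower end, phi reaches zero and the bias disappears.

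**The case against.** The strongest reply is that neither ingredient of the bias is shown for the primary gene. The protocol reports no significant A1 difference by race and describes the distributions as comparable. It reports no ethnic difference in response to bupropion or nortriptyline. In the pilot, race had no main effect on baseline startle, the genotype effect on baseline startle survived control for race, and the negative-affect results were unchanged when race was controlled. The plan also has a route to ethnicity-specific models, and a generous reading of the sentence on ethnicity and genotype could take in a three-way term with Group. Finally, the same algebra applies to gender, depression history and smoking history, so this is a general sensitivity point.

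Most of this stands as a limit on size. A reader might infer from phi = 0.22 that racial mix differs by about 22 points between A1 and A2 smokers. The documents do not support that: the interval includes zero. A reader might also infer that type I error will reach 7% or more. That needs an ethnic difference in drug effect larger than the drug effect the trial is powered for, and nothing in the documents supports one.

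The objection does not close the gap. A p-value of 0.08 in 62 people does not establish equality. The pilot gave no study drug, so its race results say nothing about drug response. The conditional models have a trigger unrelated to this bias. The three-way reading is not in the text, and the work is labelled exploratory. For DRD4, the protocol's own background documents the genotype-ethnicity link.

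**Conclusion.** The point holds as a gap in model specification. As written, the models cannot separate a gene-by-drug effect from an ethnicity-by-drug effect, and the covariate, the Ethnicity x Genotype exploration and stratification by race do not change that. Whether it matters in this trial is unknown. The bias needs both a genotype-ethnicity association and an ethnic difference in drug response. For DRD2 the first is unproven; the second is undocumented for any marker.

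On the pilot point estimate, an ethnic difference up to the size of the powered drug effect moves type I error only from 5% to about 6%; larger figures rest on larger assumptions. The documents do not support saying that the DRD2 result will be confounded. The case is somewhat stronger for DRD4, but that analysis is exploratory. This is a minor improvement worth making because it is cheap.

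**What to change.** Add Ethnicity x Group to every Hypothesis 2 model and to the exploratory gene models, with rules fixed in advance for combining small race groups. Report the Genotype x Group estimate and interval with and without the term, so that readers can see whether the gene-by-drug result depends on it. Run this regardless of whether Ethnicity x Genotype is significant. By the same logic, Gender x Group could be added as a sensitivity analysis.

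With three race groups and three arms, the cost is (3 − 1) × (3 − 1) = 4 degrees of freedom and a slight loss of precision. It uses data already to be collected and changes neither the design nor the sample size.
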